8.4.2 Adverse events

Investigators should refer to the Safety Information section of the current IB for regorafenib , including the DCSI (development core safety information), for the expected side effects of , regorafenib. As with any agent, there is always the potential for unexpected AEs, including hypersensitivity reactions. The IB will be updated if any new relevant safety data are obtained.

Therapeutic monitoring should be performed following dose selection or modification of regorafenib , in a manner consistent with the local clinical standard of care. In general, subjects should be closely monitored for side effects of all concomitant medications regardless of the path of drug elimination.

All concomitant medications must be recorded in the subject's source documentation.

Subjects must be carefully monitored for AEs. This monitoring also includes clinical laboratory tests. Adverse events should be assessed in terms of their seriousness, intensity, and relationship to the study drug, or other chemotherapy/treatment.

8.4.3 Definitions

Definition of adverse event (AE)

In a clinical study, an AE is any untoward medical occurrence (i.e. any unfavorable and unintended sign [including abnormal laboratory findings], symptom or disease) in a patient or clinical investigation subject after providing written informed consent for participation in the study. Therefore, an AE may or may not be temporally or causally associated with the use of a medicinal (investigational) product.

A surgical procedure that was planned prior to the start of the study by any physician treating the subject should not be recorded as AE (however, the condition for which the surgery is-required may be an AE if worsens compared to baseline).

- Conditions that started before signing of informed consent and for which no symptoms or treatment are present until signing of informed consent are recorded as medical history (e.g. seasonal allergy without acute complaints).
- Conditions that started before signing of informed consent and for which symptoms or treatment are present after signing of informed consent, at *unchanged intensity*, are recorded as medical history (e.g. allergic pollinosis).

- Conditions that started or deteriorated after signing of informed consent will be documented as adverse events.

Definition of serious adverse event (SAE)

An SAE is classified as any untoward medical occurrence that, at any dose, meets any of the following criteria (a – f):

- a. Results in death.
- b. Is life-threatening.

The term ‘life-threatening’ in the definition refers to an event in which the patient was at risk of death at the time of the event, it does not refer to an event which hypothetically might have caused death if it were more severe.

- c. Requires inpatient hospitalization or prolongation of existing hospitalization.

A hospitalization or prolongation of hospitalization will not be regarded as an SAE if at least one of the following exceptions is met:

- The admission results in a hospital stay of less than 12 hours.
- The admission is pre-planned.
(i.e. elective or scheduled surgery arranged prior to the start of the study)
- The admission is not associated with an AE.
(e.g., social hospitalization for purposes of respite care).

However, it should be noted that invasive treatment during any hospitalization may fulfill the criterion of ‘medically important’ and as such may be reportable as an SAE dependent on clinical judgment. In addition, where local regulatory authorities specifically require a more stringent definition, the local regulation takes precedence.

- d. Results in persistent or significant disability / incapacity.
Disability means a substantial disruption of a person’s ability to conduct normal life’s functions.
- e. Is a congenital anomaly / birth defect.
- f. Is another medically important serious event as judged by the investigator

8.4.4 Classifications for adverse event assessment

All AEs will be assessed and documented by the investigator according to the categories detailed below.

8.4.4.1 Seriousness

For each AE, the seriousness must be determined according to the criteria given in Section 8.4.3.

8.4.4.2 Intensity

The intensity of the AE is classified according to the CTCAE v4.0. Grade refers to the severity (intensity) of the AE:

CTCAE v4 Grade 1: mild; asymptomatic or mild symptoms; clinical or diagnostic observations only; intervention is not indicated.

CTCAE v4 Grade 2: moderate; minimal, local, or noninvasive intervention is indicated; limiting to age-appropriate instrumental activities of daily living (ADL; instrumental ADL refers to preparing meals, shopping for groceries or clothes, using the telephone, managing money, etc).

CTCAE v4 Grade 3: Severe or medically significant but not immediately life threatening; hospitalization or prolongation of hospitalization is indicated; disabling; limiting to self care ADL (self care ADL refers to bathing, dressing and undressing, feeding self, using the toilet, taking medications, and not bedridden).

CTCAE v4 Grade 4: life-threatening consequences; urgent intervention is indicated.

CTCAE v4 Grade 5: death due to an AE.

8.4.4.3 Causal relationship

The assessment of the causal relationship between an AE and the administration of treatment is a clinical decision based on all available information.

The assessment is based on the question whether there was a “reasonable causal relationship” to the study treatment in question.

Possible answers are “yes” or “no”.

An assessment of “no” would include:

1. The existence of a clear alternative explanation, e.g. mechanical bleeding at surgical site.

Or

2. Non-plausibility, e.g. the subject is struck by an automobile when there is no indication that the drug caused disorientation that may have caused the event; cancer developing a few days after the first drug administration.

An assessment of “yes” indicates that there is a reasonable suspicion that the AE is associated with the use of the study treatment.

Factors to be considered in assessing the relationship of the AE to study treatment include:

- The temporal sequence from drug administration: The event should occur after the drug is given. The length of time from drug exposure to event should be evaluated in the clinical context of the event.
- Recovery on drug discontinuation (de-challenge), recurrence on drug re-introduction (re-challenge):
- Subject’s response after de-challenge or subjects response after re-challenge should be considered in the view of the usual clinical course of the event in question.
- Underlying, concomitant, intercurrent diseases:
Each event should be evaluated in the context of the natural history and course of the disease being treated and any other disease the subject may have.
- Concomitant medication or treatment:
The other drugs the subject is taking or the treatment the subject receives should be examined to determine whether any of them may be suspected to cause the event in question.
- The pharmacology and pharmacokinetics of the study treatment:
The pharmacokinetic properties (absorption, distribution, metabolism and excretion) of the study treatment, coupled with the individual subject’s pharmacodynamics should be considered.

[Causal relationship to protocol-required procedure(s)]

The assessment of a possible causal relationship between the AE and protocol-required procedure(s) is based on the question whether there was a “reasonable causal relationship” to protocol-required procedure(s).

Possible answers are “yes” or “no”.

8.4.4.4 Action taken with study treatment

Any action on study treatment to resolve the AE is to be documented using the categories listed below.

8.4.4.5 Other specific treatment(s) of adverse events

- None
- Remedial drug therapy

8.4.4.6 Outcome

The outcome of the AE is to be documented as follows:

- Recovered/resolved
- Recovering/resolving
- Recovered/resolved with sequelae
- Not recovered/not resolved
- Fatal
- Unknown

8.4.5 Assessments and documentation of adverse events**8.4.5.1 Reporting of serious adverse events**

The definition of serious adverse events (SAEs) is given in Section 8.4.3.

Each serious adverse event must be followed up until resolution or stabilization, by submission of updated reports to the designated person. An isolated laboratory abnormality that is assigned grade 4, according to CTC definition, is not reportable as an SAE; unless the investigator assesses that the event meets standard ICH criteria for an SAE. CTC grade 4 baseline laboratory abnormalities that are part of the disease profile should not be reported as an SAE, specifically when they are allowed or not excluded by the protocol inclusion/exclusion criteria.

When required, and according to local law and regulations, serious adverse events must be reported to the Ethics Committee and Regulatory Authorities.

All serious adverse events should be reported to Bayer within 24 hours. In the event of such an event, the investigator should refer to the Pharmacovigilance section of the contract for reporting procedures.

The Investigator may report serious adverse drug reactions (SADRs) using either:

An ADEERS form (Adverse Event Expedited Reporting System) available at <http://ctep.cancer.gov/reporting/adeers.html>

OR

A MedWatch form available at <http://www.fda.gov/medwatch/>

All reports shall be sent electronically to:

Electronic Mailbox: [contact]

[contact]

Address: Global Pharmacovigilance - USA
Mail only: Bayer HealthCare Pharmaceuticals Inc.
[name]
[name]

Address: **[name]**
FDX or UPS only

Reports for all Bayer products can also be phoned in via our Clinical Communications Dept:

[contact]

8.4.5.2 Expected adverse events

For this study, the applicable reference document is the most current version of the investigator's brochure (IB) / summary of product characteristics.

Overview listings of frequent events that have occurred so far in the clinical development are shown in the current IB. If relevant new safety information is identified, the information will be integrated into an update of the IB and distributed to all participating sites.

The expectedness of AEs will be determined by Bayer according to the applicable reference document and according to all local regulations.

8.4.5.3 Adverse events of special safety interest

As with any new chemical entity, there is always potential for unexpected adverse events, including hypersensitivity reactions.

Based on data studies with regorafenib and from current knowledge of the pharmacological properties of other small molecule tyrosine kinase inhibitors in this drug class, as soon as there is reasonable suspicion of any of the following AEs, the investigator should immediately notify the sponsor as outlined in Section 7.4.1.4.

Reportable adverse events include:

- Acute renal failure (NCI-CTCAE version 4.0 \geq grade 3) or severe proteinuria (NCI-CTCAE version 4.0 \geq grade 3)
- Interstitial lung disease
- Acute cardiac failure
- Clinically significant bleeding (NCI-CTCAE version 4.0 \geq grade 3)
- Stevens-Johnson Syndrome and erythema multiforme

- Hepatic failure
- Reversible posterior leukoencephalopathy syndrome
- Gastrointestinal perforation or fistula

8.4.6 Pregnancies/Contraception

The effects of regorafenib on the developing human fetus at the recommended therapeutic dose are unknown. Regorafenib was embryo-lethal and teratogenic in rats and rabbits at exposures lower than human exposures at the recommended dose, with increased incidences of cardiovascular, genitourinary, and skeletal malformations. For this reason, women of child-bearing potential and men must agree to use adequate contraception (hormonal or barrier method of birth control; abstinence) prior to study entry and for the duration of study participation.

The investigator must report to Bayer any pregnancy occurring in a study subject, or in his partner, during the subject's participation in this study. The report should be submitted within the same timelines as an SAE, although a pregnancy per se is not considered an SAE.

For a study subject, the outcome of the pregnancy should be followed up carefully, and any abnormal outcome of the mother or the child should be reported.

For the pregnancy of a study subject's partner, all efforts should be made to obtain similar information on course and outcome, subject to the partner's consent.

For all reports, the forms provided are to be used.

9. Statistical methods and determination of sample size

9.1 Analysis sets

9.1.1 Safety analysis set.

The safety analysis set includes all enrolled patients who receive at least one dose of study medication.

9.1.1.1 Full analysis set.

The full analysis set includes all enrolled patients

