[name]
Email: [contact]
[contact]

[name] MD MPH

George Mason University
[name]
[name]
[name]
Email: [contact]

[name], MD PhD

George Mason University
[name]
[name]
[name]
Email: [contact]

Investigative Site

Caris Life Sciences
[name]
[name]
Email: [contact]

4. Correlative Study design

4.1 Study method overview:

The study will be conducted at the Georgetown Lombardi Comprehensive Cancer Center, Wake Forest University, and Masonic Cancer Center, University of Minnesota, and Caris Life Sciences. Patients will each be allocated a unique anonymous study number which will be noted on all tumor and peripheral blood samples.

Tumor Collection

Patient will undergo tumor biopsy prior to starting Regorafenib (at baseline). A second tumor biopsy will be obtained 2-3 weeks after starting Regorafenib. The timing of the biopsy was selected to allow for its completion before patients undergo dose reduction of regorafenib. Second biopsy can be waived in case of patient refusal, complications after the first biopsy or if the investigator deems the biopsy unsafe. All tumor samples will be labeled with the date, protocol number, and protocol assigned patient number. Tumor samples obtained at Georgetown Hospital and other sites will be collected by the staff of the biospecimen bank. Two specimens will be placed in biopsy cassettes embedded in optimal cutting temperature compound (OCT) and snap frozen within 15 min in dry ice or liquid nitrogen and subsequently stored at -80 until further use. Once study is completed, **the OCT embedded frozen core needle biopsy samples will be sent to the laboratory of [name] at George Mason University for tissue-based laser capture microdissection and protein pathway activation mapping via reverse phase protein array analysis.** The rest of the samples will be placed in formalin and then paraffin blocks will be formed to **be sent to Caris for CMI testing.** Only the baseline tumor samples should be sent to Caris (unless the baseline tumor sample did not have enough tissue to be analyzed, the second biopsy could be sent). Please see Appendix 14.1 for specimen requirements.

Blood Collection

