5.2.3 Replacement

Subjects who withdraw from the study prior to undergoing the first biopsy will be replaced.

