8.4 Safety

All subjects who receive at least one dose of study treatment will be valid for the safety analysis.

All observations pertinent to the safety of the study treatment will be recorded and included in the final report.

Safety variables include the following: AEs, laboratory changes (complete blood counts, electrolytes, chemistry, and coagulation), changes in vital signs (blood pressure, heart rate, respiratory rate, and temperature) and ECG and, in some instances, changes in chest x-ray images, as produced at the investigator's discretion (e.g., for evaluation for pneumonia).

All AEs whether considered drug-related or not, will be reported in with a diagnosis, start/stop dates, action taken, whether treatment was discontinued, any corrective measures taken, outcome, and other possible causes. For all events, the relationship to treatment and the intensity of the event will be determined by the investigator.

This trial will use the NCI-CTCAE v4.0 criteria for assessment of toxicity and SAE reporting with regard to toxicity grade.

8.4.1 Data safety Monitoring Plan:

The Georgetown Lombardi Comprehensive Cancer Center will be responsible for the data and safety monitoring of this multi-site trial. As this study is an investigator initiated exploratory study utilizing an FDA approved drug it is considered a moderate risk study which requires real-time monitoring by the PI and study team and semi-annual reviews by the LCCC Data and Safety Monitoring Committee (DSMC).

The Principal Investigator and the Co-Investigators will review the data including safety monitoring at their weekly institution based disease group meetings and on monthly teleconferences.

All Severe Adverse Events (SAEs) are required to be reported to the IRB. Based on SAEs, the IRB retains the authority to suspend further accrual pending more detailed reporting and/or modifications to further reduce risk and maximize the safety of participating patients.

Progress on the trial and the toxicities experienced will be reviewed by the LCCC Data and Safety Monitoring Committee every 6 months from the time the first patient is enrolled on the study. Results of the DSMC meetings will be forwarded to the IRB with recommendations regarding need for study closure.

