Safety analyses will be performed in all treated subjects. Descriptive statistics of safety will be presented using National Cancer Institute (NCI) Common Terminology Criteria for Adverse Events (CTCAE) version 4.0. All on-study AEs, treatment-related AEs, SAEs, and treatment-related SAEs will be tabulated using worst grade per NCI CTCAE v 4.0 criteria by system organ class and preferred term. On-study lab parameters including hematology, chemistry, liver function, and renal function will be summarized using worst grade NCI CTCAE v 4.0 criteria. For continuous safety variables, mean, standard deviation, and 95% confidence interval will be calculated at baseline and each visit.

Descriptive statistics (N, percentage for categorical variables and N, mean, std, median, min, max for continuous variables) will be used to summarize the activation status of phosphoproteins, presence and level of mutated DNA in serum at baseline, 4 and 8 weeks of study treatment. Repeated measures models may be used to explore the relationship between the level of mutated DNA in serum with clinical response.

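### Harm from the baseline research biopsy in a patient who never starts regorafenib enters no planned safety table, and in dosed patients it is not separated from drug toxicity

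*Combined protocol and SAP*

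**What the plan says.** Three places define who is in the safety analysis, and each requires a dose of drug:

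- Section 9.1.1: "The safety analysis set includes all enrolled patients who receive at least one dose of study medication".
- Section 8.4: "All subjects who receive at least one dose of study treatment will be valid for the safety analysis".
- Section 9.3.2: "Safety analyses will be performed in all treated subjects".

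The full analysis set (9.1.1.1) covers everyone enrolled, but no safety summary is assigned to it.

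The first research biopsy is taken before regorafenib starts (4.1, 7.2.1.3) and consists of at least four cores (4.2.2). A second, at day 14-21, is marked optional in 7.2.1.8 and can be waived (4.1, 7.2.1.10).

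Adverse events count from consent: section 8.4.3 defines them as occurring in a "subject after providing written informed consent for participation in the study". Section 8.4.4.3 asks for two yes/no causality judgements, one for study treatment and one for protocol-required procedures.

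The tables are listed in 9.3.2: "All on-study AEs, treatment-related AEs, SAEs, and treatment-related SAEs will be tabulated using worst grade". None uses the procedure judgement.

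On replacement, section 5.2.3 says: "Subjects who withdraw from the study prior to undergoing the first biopsy will be replaced".

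**The concern.** Regorafenib is an approved drug for this setting, obtained by prescription. A main risk that the study itself adds is the research biopsy. The protocol expects that risk: it sets clotting and platelet limits because of the biopsy (5.1.1), bars therapeutic anticoagulation for the same reason (6.5), and lets the second biopsy be waived after complications of the first (4.1).

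Yet the safety population starts from a dose of drug, and the first biopsy comes before it. A complication serious enough to keep a patient off treatment would be recorded and then left out of every safety table. The study is meant to feed larger validation trials (2.1), and their planners would look to its report for the risk of the biopsies.

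**Working it through.** The plan states no figure for biopsy harm, so the main check follows each kind of patient through the written rules.

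| Patient with a baseline-biopsy complication | Recordable AE (8.4.3) | In safety set (9.1.1, 8.4, 9.3.2) | Where the event appears |
|---|---|---|---|
| Later dosed | Yes | Yes | All-cause AE/SAE tables, not labelled as procedural |
| Never dosed, classed as enrolled | Yes | No | No safety table |
| Never dosed, classed as screening failure (5.2.2) | Yes | No | No safety table |

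The first row assumes that on-study, which 9.3.2 does not define, runs from consent as the AE definition does.

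**Status of the never-dosed patient.** The events table puts the baseline biopsy in the screening column. Section 5.2.2 calls a patient a dropout once assigned to treatment or dosed, and a screening failure before that. The documents do not settle which applies after biopsy and before dosing. The result is the same either way. Section 5.2.3 provides for replacement only before the first biopsy, so by its silence a biopsied, never-dosed patient is not replaced.

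**Is the loss informative?**

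1. Section 5.1.2 excludes a patient with a Grade 3 or higher bleed within 4 weeks before study medication.
2. Section 5.3.2 requires confirmed eligibility before therapy starts.
3. The events table requires baseline evaluations within 28 days before therapy.
4. So a Grade 3 or higher bleed from the baseline biopsy itself bars dosing for 4 weeks. By then, evaluations done before the biopsy are at or beyond the 28-day limit.
5. If the patient is then never dosed, the event leaves the tables. The omission therefore tends to select severe events.

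**Size (assumed; the documents give neither a complication rate nor the number never dosed).** Take 40 biopsied patients (the planned number, 9.4) and one serious complication in a patient who is never dosed.

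- Proportion: 1/40 = 2.5%.
- Exact lower limit: 1 − 0.975^(1/40) = 0.06%.
- Exact upper limit: the p that solves (1 − p)^40 + 40p(1 − p)^39 = 0.025, which is 13.2%.

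The planned tables would show nothing of this event.

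The chance that at least one event is left out, with u never-dosed patients and complication rate c among them, is 1 − (1 − c)^u:

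- u = 1, c = 2%: 2%.
- u = 6, c = 20%: 1 − 0.8^6 = 74%.

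These values of u and c only span a range. If complications are themselves the reason for not starting, c among the never-dosed is higher.

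**The case against.** The strongest reply is that a dosed-only set is the natural one for drug toxicity. Biopsy safety is not an objective or a named endpoint, the study is exploratory with 40 patients, and no biomarker or efficacy result changes. This stands as a reason to keep the dosed set for drug toxicity. It does not explain why the plan asks for a procedure-causality judgement and then leaves it out of every summary, when the safety endpoint (8.2.5) includes describing the safety profile.

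One could also point to section 8.4, which promises that all safety observations go into the final report. That promise is limited to the safety of the study treatment, so it does not clearly cover procedures.

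Four stronger readings are tempting, and the documents do not support them:

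- A reader might infer that safety oversight would miss these cases. Nothing ties oversight to the safety set. SAEs go to the IRB (8.4.1) and to the company within 24 hours (8.4.5.1), the DSMC reviews toxicities every 6 months (8.4.1), and AE evaluation is scheduled at screening.
- A reader might infer that all 40 baseline biopsies fall outside the safety analysis because they precede dosing. The set is defined by patient, not by time window, so harm in a patient who is later dosed is counted among all-cause events.
- A reader might infer that the plan would report a falsely low biopsy complication rate, such as 0/39. The plan produces no biopsy complication rate at all.
- A reader might take two biopsies per patient as fixed. The second is optional.

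A last point also stands. The procedure-causality item sits under a bracketed heading in 8.4.4.3, and the AE recording lists in 7.2.1.7 and 8.4 name only the relationship to study drug or treatment. It is not certain that the CRF captures it.

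**Conclusion.** The gap is real and confined to the planned analysis and final report. Under three consistent statements of the safety population, a baseline-biopsy complication in a never-dosed patient enters no safety table. In dosed patients such harm is counted but cannot be told apart from drug toxicity.

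The omission follows from the written rules. That it falls mainly on severe events is likely rather than certain: it rests on the bleeding exclusion and on the assumption that some affected patients never go on to be dosed. How many patients are involved is unknown, and the 2.5% figure is only an illustration. The change is worth making because it alters which harms are counted, at little cost.

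**What to change.** - In 9.1, add a biopsy safety set: every patient with at least one research biopsy, dosed or not, including those classed as screening failures.
- In 9.3.2, add a table of AEs and SAEs judged related to protocol-required procedures on that set. Split it by baseline and optional day 14-21 biopsy, with the number biopsied at each time point as denominator.
- Keep the dosed set for drug toxicity.
- Confirm that the CRF captures the procedure-relatedness item in 8.4.4.3.

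The cost is one set definition, one table and possibly one CRF field. No visits, procedures or patients are added. The reported complication picture may look slightly less favourable.
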